## 9. STUDY INTERVENTION DISCONTINUATION AND PARTICIPANT

### 9.1. Discontinuation of study intervention

Discontinuation from DPOS study does not mean discontinuation from the treatment, and remaining study procedures should be completed as indicated by the study protocol. Suppose a clinically significant finding is identified (including, but not limited to changes from baseline) after enrollment. In that case, the investigator or qualified designee will determine if any change in participant management is needed. Any new clinically relevant finding will be reported as an adverse event (AE).

### 9.2. Participant discontinuation/withdrawal from the Study

Participants are free to withdraw from the Study at any time upon request.

An investigator may discontinue or withdraw a participant from the Study for the following reasons:

- Pregnancy that is not from an embryo transfer cycle
- Significant study intervention non-compliance
- If any clinical adverse event (AE), laboratory abnormality, or other medical condition or situation occurs such that continued participation in the Study would not be in the best interest of the participant
- Disease progression which requires discontinuation of the study intervention
- If the participant meets an exclusion criterion (either newly developed or not previously recognized) that precludes further study participation

The reason for participant discontinuation or withdrawal from the Study will be recorded on the Case Report Form (CRF). Subjects who sign the informed consent form and are randomized but do not receive the study intervention may be replaced. Subjects who sign the informed consent form, and are randomized and receive the study intervention, and subsequently withdraw, or are withdrawn or discontinued from the Study, will not be replaced.

### **9.3. Lost to follow-up**

A participant will be considered lost to follow-up if she fails to return for scheduled visits and is unable to be contacted by the study site staff.

The following actions must be taken if a participant fails to return to the clinic for a required study visit:

- The site will attempt to contact the participant, reschedule the missed visit, counsel the participant on the importance of maintaining the assigned visit schedule, and ascertain if the participant wishes to and/or should continue in the Study.
- Before a participant is deemed lost to follow-up, the investigator or designee will make every effort to regain contact with the participant (where possible, 3 telephone calls and, if necessary, a certified letter to the participant's last known mailing address or local equivalent methods). These contact attempts should be documented in the participant's medical record or study file.
- Should the participant continue to be unreachable, she will be considered to have withdrawn from the Study with a primary reason of loss to follow-up.

## **10. STUDY ASSESSMENT AND PROCEDURES**

### **10.1. Feasibility of Study**

IVFTA-HCM is a recognised center in Vietnam with high volume and modern equipment. IVFTA-HCM has a volume about 1700 - 2000 cycles per year. Of these, 67% of patients under 37 years old and 45% had a low ovarian reserve. Frozen embryo transfer is 97% of all cycles. The embryo and gamete cryopreservation system at IVFTA-HCM is well-established for freezing requirements in the oocyte collection strategy. RTAC code of practice was applied in quality management.

### **10.2. Safety and other assessments**

The investigator will inform subjects and the reviewing accredited medical research ethics committee if anything occurs, based on which it appears that the disadvantages of participation may be significantly greater than was foreseen in the research proposal. The Study will be suspended pending further review by the accredited medical research ethics committee, unless suspension would jeopardize the subjects' health. The investigator will take care that all subjects are kept informed

## **11. ADVERSE EVENTS AND SERIOUS ADVERSE EVENTS**

### **11.1. Adverse Events and adverse drug reactions**

Adverse events (AE) are defined as any undesirable experience occurring to a subject during the trial, whether or not considered related to the intervention.

An adverse drug reaction (ADR) is defined as an appreciably harmful or unpleasant reaction resulting from an intervention related to the use of a medicinal product; adverse effects usually predict hazard from future administration and warrant prevention, or specific treatment, or alteration of the dosage regimen, or withdrawal of the product

## **11.2. Reporting of adverse events**

### **11.2.1. AE Recording**

All adverse events reported spontaneously by the subject or observed by the investigator or their staff will be recorded. Any AE should be recorded on the Adverse Events form in the CRF and source documents. In every visiting, AE/SAE will be recorded by subject or observed by medical staff. The AE/SAE related medication also will be asked routinely in the oocyte pick-up day (**Visit 7**) of every ovarian stimulation cycle.

AEs will be collected from the time the subject signed the study specific informed consent until the last visit (**Visit 13**) according to the pregnancy outcomes (the primary endpoint is the ongoing pregnancy).

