##### 4.2. Secondary objectives:

- To compare the characteristics of ovarian stimulation between DPOS and GnRHanta protocol, including LH, Estradiol, and Progesterone profile (Day 1, day 5, and day 8 of ovarian stimulation, final oocyte maturation day, and 12 hours after the final oocyte maturation injection), premature LH rate, the duration of ovarian stimulation and the total dose of FSH, the number of ovarian stimulation cycles.

- To compare the outcomes of the ovarian stimulation between DPOS and GnRH protocol, including number of cumulus-oocyte complexes, number of MII oocytes, oocyte survival rate, fertilization rate, embryo-cleavage rate, blastocyst rate, top-quality blastocyst rate, blastocyst survival rate, implantation rate, positive pregnancy rate, clinical pregnancy rate, early miscarriage rate, multiple pregnancy rate, ectopic pregnancy rate.
- To compare the drop-out rate of DPOS and GnRH protocol in accumulation oocyte cycles of patients with low ovarian reserve
- To assess the safety of DPOS and GnRH protocol in accumulation oocyte cycles of patients with low ovarian reserve.
- To compare the quality of life during ART treatment based on WHO-BRIEF questionnaire

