## 5. STUDY DESIGN

This open-label, randomized, controlled, multi-center clinical trial compares the efficacy and safety of the oral Dydrogesterone primed ovarian stimulation versus fixed gonadotropin-releasing hormone antagonist protocol for accumulating oocytes in patients with low ovarian reserve.

- Study Type: Interventional (Clinical Trial)
- Estimated Enrollment: 730 participants (365 per arm)
- Allocation: Randomized
- Intervention Model: Parallel Assignment
- Masking: Open-label
- Primary Purpose: Treatment
- Official Title: Dydrogesterone primed ovarian stimulation versus fixed gonadotropin-releasing hormone antagonist protocol for accumulation of oocyte in patients with low ovarian reserve: A randomized controlled trial

The Study will be conducted according to the following scheme:

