#### *7.3.5. Endometrium preparation and embryo transfer*

At **Visit 9**, all patients undergoing FET will receive oral estradiol valerate (Valiera®; Laboratories Recalcine) 6 mg/day from the 2nd to 4th day of menses for 6 days. The endometrial thickness will be monitored from day six onwards. From day 8-9 of menses, the estradiol dose could be adjusted to 12mg/day according to the development of the

endometrium. Progesterone will be started when endometrial thickness reaches 8 mm or more. Patients will receive micronized Progesterone (Cyclogest® 400mg; Actavis) at the dose of 400mg twice daily (morning and evening) plus dydrogesterone (Duphaston 10mg) at the dose of 10mg twice daily (morning and evening). Estradiol valerate will be decreased to 4 - 8mg/day when starting Progesterone. A single embryo will be thawed on the day of embryo transfer after six or seven days of Progesterone, depending on day-5 or day-6 embryo. After thawing, surviving embryos will be transferred into the uterus under ultrasound guidance. Estradiol and Progesterone will be continued until the day of the pregnancy test. If the pregnancy test is positive, the patients will continue to use 800 mg micronized Progesterone or 800 mg micronized Progesterone plus 20 mg dydrogesterone until 7 weeks of gestation. The blastocyst will be thawed on embryo transferring day (**Visit 10**) according to the CRYOTEC® Method. After warming, the survival blastocyst is evaluated. Blastocyst cryo-survival be defined as at least 75% of cells perceived to be intact after thawing (40). After thawing, the embryo will be cultured in a CXCM medium (37oC, CO2 6%, O2 5%). The embryo will be transferred to the uterus two hours later under ultrasound.

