#### 7.4.2. *Pregnancy outcome follow-up*

Serum hCG will be measured 11 days after embryo transfer (**Visit 11**), and if positive, an ultrasound scan of the uterus will be performed at gestational weeks 7 (**Visit 12**) and 12 (**Visit 13**). At 11–12 weeks of gestation, participants will be referred to the IVFTA HCM - Tam Anh TP. Ho Chi Minh General hospital and IVFTA – Tam Anh General hospital for prenatal care. For those who cannot participate in the prenatal care program at Tam Anh TP. Ho Chi Minh General hospital or Tam Anh General hospital, for any reason, will contact the participants via telephone/email to collect data. We also ask these participants to scan the results of each visit in every contact.

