Miscarriage	Complete loss of clinical pregnancy at 12 weeks of gestation
Multiple pregnancy rate	Multiple pregnancy rate is explained as two or more gestational sacs or positive heartbeats by transvaginal sonography 5 weeks after embryo placement
Ectopic pregnancy rate	Ectopic nidation of pregnancy confirmed by sonography or laparoscopy at 12 weeks of gestation
OHSS	Ovarian hyperstimulation is diagnosed according to RCOG guideline 2016
Known Adverse events regarding medications	
Adverse events regarding medications according to local information products - including:
 
 
• Duphaston: Abdominal pain, bloating, severe headache, dizziness, depression, hot flushes, abnormal vaginal discharge, joint pain, urinary problems or nausea, fatigue or extreme tiredness, somnolence or sleepiness, vaginal hemorrhage, pruritus (severe itching of the skin).
 
• Orgalutran: redness, pain or swelling at injection site, headache, nausea, tiredness.
 

	
 
• Diphereline: nausea, tiredness, mood changes, depression, redness, swelling, pain and /or bruising at the injection site, swelling of the hands and feet (edema) muscle and bone pain, pain in arms and legs, dizziness, headache, impotence, loss of libido.
 
• Ovitrelle: injection site, headache, vomiting, nausea (feeling sick), abdominal (belly) pain, abdominal distension (feeling of bloating)
 
• Valiera: Headache, nausea, breast pain, abdominal cramp, bloating, vaginal spotting.
 
• Cyclogest: Abdominal distension (swelling in the abdomen), abdominal pain, constipation, sleepiness, tiredness, hot flush, breast pain.
 
• IVF-M: Headache, injection site pain, injection site allergic reaction, abdominal pain, abdominal cramps or nausea.
 

Drop-out	Drop-out is defined as any patient discontinuing the Study or the investigator withdrawing them from the Study for any reason.
Quality of life score	Quality of life is assessed by Vietnamese WHO-BRIEF questionnaire

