#### *12.3.3. Secondary outcome*

For continuous variables, results will be shown as mean (SD) and between-group differences will be considered using Student's t-test. For dichotomous outcomes, relative risk (RR) and 95% confidence interval (CI) values will be calculated.

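### The adverse event endpoint has no phase limit although the safety objective concerns the accumulation cycles, so a comparison to Visit 13 is diluted by a transfer phase in which both arms take the same drugs, including dydrogesterone

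*Protocol*

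**What the plan says.** Section 5 makes safety a comparison between arms: the trial "compares the efficacy and safety of the oral Dydrogesterone primed ovarian stimulation versus fixed gonadotropin-releasing hormone antagonist protocol". Section 4.2 sets the scope: "To assess the safety of DPOS and GnRH protocol in accumulation oocyte cycles of patients with low ovarian reserve". The synopsis has the same objective. The sentence that introduces Table 2 in section 8 also mentions safety and the oocyte accumulation period together, although the period may belong there only to quality of life.

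The endpoint itself is a row of Table 2: "Adverse events regarding medications according to local information products - including", followed by a list of products. The list covers the stimulation and trigger drugs (Duphaston, Orgalutran, Diphereline, Ovitrelle, IVF-M) and also Valiera and Cyclogest. No phase or onset window is given.

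Section 11.2.1 says that "AEs will be collected from the time the subject signed the study specific informed consent until the last visit", namely Visit 13, and links that end point to the pregnancy outcome. It adds a routine question on medication-related events at Visit 7 of every stimulation cycle. Section 7.4.2 makes the later visits depend on the hCG test: "and if positive, an ultrasound scan of the uterus will be performed at gestational weeks 7" and 12.

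Section 7.3.5 gives estradiol valerate to every woman having a frozen transfer, then micronized progesterone "plus dydrogesterone (Duphaston 10mg) at the dose of 10mg twice daily", with no distinction by arm. Section 12.3.3 says of secondary outcomes: "For dichotomous outcomes, relative risk (RR) and 95% confidence interval (CI) values will be calculated". It names no window.

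**The concern.** The randomized contrast is the stimulation regimen. It ends with the last stimulation cycle. From Visit 9 the two arms are treated alike, so events after that point carry little information about which regimen is better tolerated.

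Two features of the text make the added period awkward. Dydrogesterone is both the experimental drug and part of the luteal support given to everyone, so women in the antagonist arm can also have a true Duphaston reaction. The event lists also overlap: nausea, headache and bloating stand under Duphaston and Valiera, while abdominal pain, sleepiness, tiredness and hot flushes stand under Duphaston and Cyclogest. Neither the product nor the type of event shows which phase it belongs to. Only the onset date does.

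At stake is a safety comparison that leans towards similarity because of how events are counted. For safety, that is the unfavourable direction of error.

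**Working it through.** The protocol states no event rate, power or margin for adverse events, so it has no figure of its own to reproduce. The check has three parts.

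**1. Objective against endpoint.** The objective concerns the accumulation cycles. Valiera and Cyclogest first appear in section 7.3.5, at endometrial preparation, so they cannot cause events during accumulation. By naming them, Table 2 takes the endpoint beyond the period in its objective. This is something the text states, not merely something it leaves open.

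**2. How much of the window has no contrast.** Nominal days from section 5: Visit 9 = 90, Visit 11 = 121, Visit 13 = 198.

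- Woman followed to Visit 13: (198 − 90)/198 = 55% of days fall after Visit 9.
- Woman whose last visit is the pregnancy test: (121 − 90)/121 = 26%.

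These are shares of days, not of events. They are approximate because the nominal days do not change with the number of stimulation cycles.

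**3. Effect on the comparison (illustration only).** Let p be a woman's risk of an event during accumulation, and let q be an independent later-phase risk that is equal in both arms. Then:

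- whole-study risk = 1 − (1 − p)(1 − q)
- risk difference = (p_A − p_B)(1 − q)

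Both arms' risks are scaled by (1 − q) and then increased by q, so under these conditions the RR always moves towards 1. Power is for the two-sided 5% normal test of two proportions with 365 per arm (section 12.1) and pooled variance under the null. The values of p and q are assumed. With p = 30% v 20%:

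| q | Risks | Difference (points) | RR | Power |
|---|---|---|---|---|
| 0 (accumulation only) | 0.300 v 0.200 | 10.0 | 1.50 | 88% |
| 0.1 | 0.370 v 0.280 | 9.0 | 1.32 | 74% |
| 0.2 | 0.440 v 0.360 | 8.0 | 1.22 | 60% |
| 0.3 | 0.510 v 0.440 | 7.0 | 1.16 | 47% |
| 0.5 | 0.650 v 0.600 | 5.0 | 1.08 | 29% |

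With p = 15% v 10%, the RR goes from 1.50 to 1.24, 1.14, 1.09 and 1.05, and power from 53% to 32%, 22%, 16% and 10%.

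**4. Does pregnancy-dependent follow-up matter between arms?** Take the rates in section 12.1 (45% control, 40–42% DPOS) as the share of women followed to day 198, and let the rest end at day 121. Mean follow-up is then:

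- control: 121 + 77 × 0.45 = 155.65 days
- DPOS: 121 + 77 × 0.40 = 151.80 days, or 121 + 77 × 0.42 = 153.34 days

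The gap is 3.85 or 2.31 days, that is 2.5% or 1.5%. Now suppose no regimen effect, an assumed accumulation risk of 20% and an assumed late risk r among women followed to Visit 13. The spurious difference is 0.8 × r × (0.45 − 0.40 or 0.42). For r from 0.1 to 0.5 this is 0.2 to 2.0 points, which is small.

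**The case against.** The strongest reply is that the onset window of an adverse event table belongs in the statistical analysis plan, which section 12.3 promises before data lock. Section 11.2.1 governs collection, not analysis. With onset dates and the Visit 7 question in each cycle, the phases can be separated later and no data are lost. This stands as far as collection goes, and it keeps the point small. It does not clear Table 2, which presents itself as the full definition and includes transfer-phase products. The Visit 7 question is a way of collecting events, and nothing makes it the comparison window. The causality grading in section 11.2.2 does not help with dydrogesterone, which both arms take at transfer.

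A second reply is that the phrase about accumulation cycles may describe the setting rather than a time window. The drop-out objective uses the same phrase, yet Table 2 defines drop-out over the whole study. A whole-strategy safety comparison is also legitimate, and section 11.3.2 counts serious pregnancy complications as serious events. This stands too, and it is why the whole-study table should stay.

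Third, section 12.3.3 does not name adverse events or one any-event RR per woman. That is also right. Such an RR is a natural reading and serves the illustration, but the text does not commit to it.

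**Conclusion.** The mismatch between the safety objective and the Table 2 endpoint is in the text. A between-arm comparison of events to Visit 13 would be diluted towards no difference. The direction holds whenever the later-phase risk is independent and equal across arms. The size is not known: RR 1.50 falling to 1.32–1.08 rests wholly on assumed rates, and the protocol states no power or margin for adverse events that would be breached. This is a cheap improvement, not a flaw that threatens the trial.

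Three stronger readings are tempting but not supported:

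- A reader might infer that follow-up tied to pregnancy materially biases the arm comparison. At the protocol's own rates the arms differ by about 2 to 4 days of about 156.
- A reader might infer that transfer-phase events overwhelm those due to the regimen. With no rates in the protocol this cannot be shown, and at an assumed q of 0.2 the RR is still 1.22.
- A reader might infer that collection stops at about Day 77 for a woman with no blastocyst. Section 8 only classes such cycles as failures for the primary endpoint, and section 11.2.1 sets no such stop.

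**What to change.** In Table 2 and section 12.3.3, define the between-arm adverse event comparison that answers the safety objective. It should count events with onset from the first dose of the allocated regimen to the start of endometrial preparation (Visit 9), or to exit if earlier. State that the first gonadotropin dose at Visit 2 opens the window, so that it starts at the same point in both arms although the antagonist begins on stimulation day 5. Report events from Visit 9 to Visit 13 in a separate table by arm. Leave collection to Visit 13, serious event reporting and the whole-study table unchanged.

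The cost is one definition sentence and one extra table split by onset date. No new data or visits are needed. The headline event count will be lower, which the report should explain. The window should be fixed before data lock, because in an open-label trial a later choice could look driven by the results.

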### **11.2.2. AE assessment**

Each AE is to be evaluated by the investigator for duration, severity, seriousness and causal relationship to the investigational drug. The action taken with study drug, the concomitant treatment/therapy introduced and the outcome, and as well as whether the event led to study termination will also be recorded.

#### **Severity**

The severity of the AE should be characterized as ““mild, moderate or severe”” according to the following definitions:

- Mild events are usually transient and do not interfere with the subject's daily activities.
- Moderate events introduce a low level of inconvenience or concern to the subject and may interfere with daily activities.
- Severe events interrupt the subject's usual daily activity.

#### **Drug-Event Relationship**

The causal relationship between the study drug and the AE should be characterized according to the following:

- Unrelated – there is not a reasonable possibility that the study drug caused the AE.
- Unlikely – suggests that only a remote connection exists between the study drug and the event. Other conditions, including concurrent illness, progression or expression of the disease state or reaction to concomitant medication, appear to explain the AE.
- Possible – suggests that the association of the AE with the study drug is unknown, however, the event is not reasonably supported by other conditions.
- Probable – suggests that a reasonable temporal sequence of the AE with drug administration exists and, in the Investigator's clinical judgment, it is likely that a causal relationship exists between the drug administration and the AE, and other conditions (concurrent illness, progression or expression of the disease state, or concomitant medication reactions) do not appear to explain the AE.

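### The adverse-event causality scale in 11.2.2 has no grade for an event that both the study drug and another cause could reasonably explain

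*Protocol*

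**What the plan says.** Protocol section 11.2.2 has the investigator evaluate each adverse event for, among other things, "seriousness and causal relationship to the investigational drug". Under Drug-Event Relationship it gives four grades:

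- **Unrelated:** "there is not a reasonable possibility that the study drug caused the AE".
- **Unlikely:** the grade "suggests that only a remote connection exists between the study drug and the event", and a second sentence adds: "Other conditions, including concurrent illness, progression or expression of the disease state or reaction to concomitant medication, appear to explain the AE".
- **Possible:** the grade suggests that "the association of the AE with the study drug is unknown, however, the event is not reasonably supported by other conditions".
- **Probable:** timing fits, a causal link is judged likely, and alternative explanations, expressly including reactions to concomitant drugs, do not seem to account for the event.

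Section 7.3.1 gives both arms hMG and a dual trigger of Ovitrelle and Diphereline. Section 7.3.5 gives dydrogesterone to all patients in the transfer cycle, whatever their arm. Table 2 in section 8 lists known reactions by product. For the antagonist it reads "Orgalutran: redness, pain or swelling at injection site, headache, nausea, tiredness". For Diphereline it includes nausea, tiredness, headache and "redness, swelling, pain and /or bruising at the injection site".

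**The concern.** The two upper grades both require that nothing else reasonably explains the event. The two lower grades both require that the link to the study drug is remote or absent. A common kind of event lies between them: the study drug is a reasonable suspect, and so is something else the woman is taking. In a trial where every participant receives several drugs with similar listed reactions, this is an ordinary situation.

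Causality must be graded for every event, comparing the safety of the two protocols is a secondary objective, and section 11.1 separates an adverse drug reaction from an adverse event by causation. With no fitting grade, investigators who know the allocation have to improvise. The likely result is inconsistent grading, possibly drifting to 'Unlikely', which is the only grade whose wording accepts another explanation. The terms 'investigational drug' and 'study drug' are also not defined for the control arm, and dydrogesterone in the transfer cycle makes them ambiguous in both arms.

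**Working it through.** The plan states no figure on this point, so there is none to reproduce. Two checks apply.

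**1. Logic of the grades.** Take an event with (a) a reasonable link to the study drug and (b) another reasonable explanation, such as a co-administered drug.

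| Grade | Requirement that matters | Met? |
|---|---|---|
| Unrelated | no reasonable possibility of a study-drug cause | No, fails on (a) |
| Unlikely | link only remote, and another cause appears to explain the event | No, fails on (a), although (b) is met |
| Possible | no reasonable support from other conditions | No, fails on (b) |
| Probable | other conditions do not appear to explain the event | No, fails on (b) |

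Grades that fit: 0 of 4. 'Possible' does not itself name concomitant medication as an 'other condition', but 'Unlikely' and 'Probable' both do, so the same meaning is taken for all three.

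**2. Are such events likely?** Inputs are the reaction lists in Table 2, split into single terms: 14 for dydrogesterone (Duphaston) and 6 for the antagonist (Orgalutran, taken to be the ganirelix product). IVF-M is assumed to be the hMG product; the protocol does not say so. The share is listed terms that also appear for the background drugs, divided by all listed terms. Where a range is given, the higher value also matches joint pain with muscle and bone pain, and vaginal haemorrhage with vaginal spotting.

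| Background drugs counted | Dydrogesterone | Antagonist |
|---|---|---|
| hMG only | 3/14 = 21% | 3/6 = 50% |
| hMG plus trigger drugs | 7/14 = 50% to 8/14 = 57% | 6/6 = 100% |
| All, including the transfer cycle (Valiera, Cyclogest) | 9/14 = 64% to 11/14 = 79% | 6/6 = 100% |

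The three dydrogesterone terms shared with hMG are abdominal pain, headache and nausea. The trigger drugs add bloating, dizziness, depression and tiredness. The three antagonist terms shared with hMG are injection-site pain, headache and nausea. Diphereline adds injection-site redness, injection-site swelling and tiredness. Headache and nausea are thus shared in both arms even before the trigger.

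**The case against.** The strongest reply is that this is a wording gap with little consequence. Under 11.1, events count as adverse events whether or not they are thought related. All of them go into periodic reports (11.2.3). Serious events are reported regardless of causality (11.3.2). Interim safety rests on serious events (12.3.6). The medication-event endpoint in Table 2 is defined by product information, and the protocol specifies no between-arm count of drug-related events. The DSMB adjudicates events itself (12.3.5), and nothing ties its review to the investigator's grade. All of this stands and limits the harm to the causality data.

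A second reply is that a shared term on two product lists does not mean that the other drug explains a given case. This also stands. The grades call for judgement case by case, and timing, route or injection site can separate causes: hMG is described as intramuscular and the antagonist as subcutaneous.

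Three stronger readings are tempting, but the protocol does not support them.

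- *Events with two plausible causes must be graded 'Unlikely'.* No sentence directs this, and 'Unlikely' needs a remote link, so such events have no grade.
- *No listed antagonist reaction could ever be graded 'Possible' or 'Probable', because Diphereline shares all six terms.* Adverse events are recorded at every visit, with the extra medication question at Visit 7. In the first cycle the antagonist starts on day 5 and Diphereline comes only at the trigger, around day 10 ± 2. It cannot explain a reaction that precedes it.
- *Most listed reactions are affected, and unequally by arm.* For dydrogesterone the strict share up to Visit 7 is exactly half. The figures count terms, not events, and the protocol gives no event rates.

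**Conclusion.** The gap is real and follows from the four definitions alone: an event with two reasonable causes, one of them the study drug, meets none of them. The overlapping lists make such events likely in both arms. That expectation rests on matching terms by name and on taking IVF-M as hMG and Orgalutran as ganirelix; the logic of the grades does not depend on these assumptions.

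The consequence is limited to recorded and reported causality. A reader might infer that drug-related events will be undercounted in a way that disfavours dydrogesterone. The protocol supports neither a size nor a direction for such a difference: event rates are not given, 'study drug' is undefined for the control arm, and both arms receive dydrogesterone in the transfer cycle. Differential grading is conceivable in an open-label trial, but it is not shown. The point still merits correction, because the rule applies to every adverse event and the remedy is short.

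**What to change.** Amend 11.2.2 and the matching case report form guidance in three places:

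1. Reword 'Possible' as a reasonable possibility that the study drug caused or contributed to the event, although other conditions or concomitant medication could also explain it.
2. Keep 'Unlikely' for events where another cause is clearly more likely.
3. State what 'study drug' means in each arm, including how dydrogesterone in the transfer cycle is treated.

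The direct cost is a short amendment with ethics approval. Somewhat more events will appear as possibly related in both arms, and events graded before and after the change must be distinguished in the data and in reports. At the August 2024 count in the summary of changes, 272 of 730 participants were recruited. On that count, 730 − 272 = 458 (63%) were still to enter; how many would be graded wholly on the new wording depends on when it takes effect.

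I would not ask for a separate grade for each co-administered product, which adds burden to every event. Nor would I ask for re-grading of past events: with allocation known, it could itself introduce differential attribution.
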